#### **4.7.2 Adverse events**

##### **General common rules for adverse events**

All adverse events (AEs) will be coded to a lower-level term (LLT), preferred term (PT), and associated primary system organ class (SOC) using the MedDRA version currently in effect at Sanofi at the time of database lock.

The AE tables will be sorted as indicated in [Table 5](#).

**Table 5 - Sorting of AE tables**

AE presentation	Sorting rules
SOC and PT	By the primary SOC and PT alphabetical order

### **Analysis of all adverse events**

The safety overview after injection with the details below will be generated:

- Within 28 days after vaccine injection
  - Immediate unsolicited AE and adverse reaction (AR)
  - Solicited reaction
  - Solicited injection site reaction
  - Solicited systemic reaction
  - Unsolicited AE and AR
  - Unsolicited non-serious AE and AR
  - Unsolicited non-serious injection site AR
  - Unsolicited non-serious systemic AE and AR
  - AE leading to study discontinuation
  - Serious adverse event (SAE)
  - Death
  - AE of special interest (AESI)
- During the study
  - SAE
  - Death
  - AESI

### **Solicited reactions**

The following summaries of solicited reactions within 7 days after vaccine injection will be presented using the terms prelisted in CRB:

- All and Grade 2 or 3 solicited reaction, solicited injection site reaction, and solicited systemic reaction
- Solicited reaction, each solicited injection site reaction (injection site pain, injection site erythema, injection site swelling, injection site induration, and injection site bruising), and solicited systemic reaction (fever, headache, malaise, myalgia, and shivering)

- Solicited injection site reactions (injection site pain, injection site erythema, injection site swelling, injection site induration, and injection site bruising) and solicited systemic reactions (fever, headache, malaise, myalgia, and shivering) by following category:
  - By maximum intensity
  - By time of onset period
  - By range of number of days of occurrence during the solicited period (for any solicited reaction and Grade 3 solicited reactions)
  - By range of overall number of days of occurrence for the reactions still ongoing at D8 after vaccine injection
  - By action taken

### **Unsolicited AEs**

The summary of unsolicited AEs within 7 days after vaccine injection with the details below will be generated:

- Immediate unsolicited AE and AR (any and Grade 3)
- Unsolicited AE and AR
- Unsolicited non-serious AE and AR (any and Grade 3)
- Unsolicited non-serious injection site AR (any and Grade 3)
- Unsolicited non-serious systemic AE and AR (any and Grade 3)
- SAE
- AESI

The summary of unsolicited AEs within 28 days after vaccine injection will also be generated.

The unsolicited non-serious AEs and ARs within 28 days after vaccine injection will also be summarized by maximum intensity, time of onset, and duration.

The AE summaries after vaccine injection of [Table 6](#) will be generated with number (%) of subjects experiencing at least one event. In the summaries, the 95% CI of proportion and number of AE/ARs will also be presented.

The all and related SAEs within 28 days after vaccine injection and during the study will also be summarized by seriousness criterion and outcome.

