12.1.2.2 Statistical Methods

Safety

Safety results will be analyzed descriptively for subjects in the safety analysis set (SafAS) who received QIV-HD or QIV-SD. Solicited reactions (solicited injection site and systemic reactions), unsolicited AEs, SAEs, and AESIs will be summarized. The main parameters will be described with 95% CIs (Clopper-Pearson method) (33).

- Unsolicited systemic AEs occurring within 30 minutes of injection (immediate unsolicited AEs)
- Solicited injection site reactions (pain, erythema, swelling, induration, and brusing) occurring within 7 days after the day of injection (D0 to D7) according to presence, time to onset, number of days of occurrence, maximum intensity (Grade 1, Grade 2, or Grade 3), action taken, and whether the reaction led to early termination from the study. When more than 1 intensity level is reported within a time period, the highest intensity will be used.
- Solicited systemic reactions (fever, headache, malaise, myalgia, and shivering) occurring within 7 days after the day of injection (D0 to D7) according to presence, time to onset, number of days of occurrence, maximum intensity (Grade 1, Grade 2, or Grade 3), action taken, and whether the reaction led to early termination from the study. When more than 1 intensity level is reported within a time period, the highest intensity will be used.
- Unsolicited AEs occurring within 28 days after the day of injection by system organ class (SOC) and PT, time to onset, duration, maximum intensity (Grade 1, Grade 2, or Grade 3), relationship to vaccination (for systemic AEs only), and whether the event led to early termination from the study.
- All SAEs that occur throughout the study by SOC and PT, time to onset, seriousness criteria, relationship to vaccination, outcome, and whether the event led to early termination from the study.
- All AESIs reported throughout the study by SOC and PT and relationship to vaccination.

Immunogenicity

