**Table 6 - Analyses of adverse events**

Type of AE	MedDRA levels
All unsolicited AE within 28 days	Primary SOC and PT
All unsolicited AR within 28 days	Primary SOC and PT

Type of AE	MedDRA levels
Unsolicited AEs within 28 days occurring in >1% of subjects	Primary SOC and PT
Unsolicited non-serious AE within 28 days	Primary SOC and PT
Unsolicited non-serious AR within 28 days	Primary SOC and PT
All and related AE leading to study discontinuation within 28 days	Primary SOC and PT
SAE	Overview a
	Primary SOC and PT

a Will include the following AE categories: all SAEs and related SAEs within 7 days after vaccine injection, within 28 days after vaccine injection, and during the study

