### ***Time of onset***

Time of onset is derived from the start date of the unsolicited non-serious AE provided in the clinical database and the date of the vaccination:

Start date of the unsolicited non-serious AE – date of vaccination.

The time of onset should be considered as missing only if one or both of the dates are missing or partially missing.

The unsolicited non-serious AEs will be analyzed “Within 28 days”, which corresponds to AEs with a time of onset between 0 and 28 days after vaccination or missing. An AE with missing time of onset will be considered to have occurred just after the vaccination indicated by the visit number, so will be included in these tables.

Note: Unsolicited non-serious AE that occurred before vaccination (negative time of onset) or with a time of onset higher than defined above ( $>28$  days) will not be included in analysis, but will be listed separately.

Time of onset will be displayed as follows:

- D0-D3
- D4-D7
- D8-D14
- $\geq$ D15
- Missing

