#### **5.4.2.3 SAEs**

##### ***Time of onset***

Time of onset will be computed using the same methodology than for unsolicited non-serious AEs described in [Section 5.4.2.2](#).

SAEs will be analyzed throughout the study using the following periods:

- Within 28 days after vaccine injection
- During the study (i.e., all SAEs occurred during the study)

An SAE with missing time of onset will be considered to have occurred just after the vaccination indicated by the visit number, and will be included in these tables.

Note: SAEs that occurred before vaccination (negative time of onset) will not be included in analysis but will be listed separately.

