## ***Start Date and Stop Date***

Missing or partial missing start dates for unsolicited AEs will remain missing and not be imputed. If either the start or stop date is missing or partially missing, the time of onset will be considered to be missing. Nevertheless unsolicited AEs with missing time of onset will be included in analyses according to the visit collected.

Missing or partially missing stop dates for AEs (solicited reactions and unsolicited AEs) will remain missing and not be imputed.

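### The SAP plans 7-day summaries of unsolicited AEs, SAEs and AESIs without defining the window; its only placement rule for undated events, if carried over, counts some provably later events in week 1.

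*SAP*

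**What the plan says.** **Planned outputs.** SAP 4.7.2 (Unsolicited AEs) states: "The summary of unsolicited AEs within 7 days after vaccine injection with the details below will be generated". The listed details include SAEs and AESIs. The footnote to Table 6 adds an SAE overview covering "all SAEs and related SAEs within 7 days after vaccine injection, within 28 days after vaccine injection, and during the study". The protocol has no 7-day summary of these events. Section 12.1.2.2 plans "Unsolicited AEs occurring within 28 days after the day of injection by system organ class (SOC) and PT", and SAEs and AESIs over the whole study.

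**Windows defined.** For unsolicited non-serious AEs, SAP 5.4.2.2 defines only the 28-day window, "which corresponds to AEs with a time of onset between 0 and 28 days after vaccination or missing". For SAEs, SAP 5.4.2.3 lists two periods: within 28 days and during the study.

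**Undated events.** Under SAP 5.4.2.2, onset is the start date minus the vaccination date, and is missing only if one of those two dates is missing or partial. Then "An AE with missing time of onset will be considered to have occurred just after the vaccination indicated by the visit number". SAP 5.4.2.3 repeats this for SAEs: "An SAE with missing time of onset will be considered to have occurred just after the vaccination indicated by the visit number". SAP 5.4.4.1 (Start Date and Stop Date) says "Missing or partial missing start dates for unsolicited AEs will remain missing and not be imputed". It adds that onset is missing if either the start or the stop date is incomplete, and that such AEs enter the analyses by the visit at which they were collected.

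**The concern.** The placement rule suits the periods it was written for. Collection ends at V02, so an event of unknown date nearly always belongs in a 28-day or whole-study table. A 7-day table asks a different question, namely whether the event came early. A rule that places undated events just after vaccination can only add events to that table; it never removes one.

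Three things follow if programmers apply the rule there:

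- An event with a known month and an unknown day is treated as wholly undated, even when the month excludes D0 to D7.
- The time-of-onset display in SAP 5.4.2.2 has its own row for missing onset. The same non-serious AE would be in week 1 in one table and of unknown onset in another.
- SAP 5.4.4.1 sets missing causality to related. An SAE lacking both a full start date and a causality entry would therefore appear as a related SAE within 7 days. The documents give no indication of how often that would happen.

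**Working it through.** The plan states no figure on this point, so there is none to reproduce. The check applies the SAP rules to calendar dates.

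**1. A partial start date**

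- Vaccination: 21 October 2020, the first planned inclusion date (Protocol 5.1.5).
- AE start: November 2020, day missing.
- Earliest possible onset: 1 November − 21 October = 11 days.
- SAP 5.4.2.2 and 5.4.4.1: start date partial, not imputed, onset missing.
- Placement rule: just after vaccination, hence inside D0 to D7.
- Onset display in SAP 5.4.2.2: row for missing onset.

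The recorded month rules out week 1, but no rule uses it.

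**2. A complete start date with no stop date**

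- AE starts on D20 and is still ongoing. Protocol 9.2.2.3.3 (footnote on stop dates) treats an AE with no stop date as ongoing at study end.
- SAP 5.4.2.2: start and vaccination dates are complete, so onset = 20 days.
- SAP 5.4.4.1: the stop date is missing, so onset is missing.

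The two sections contradict each other. If 5.4.4.1 is followed and the placement rule is then applied, an AE known to start on D20 falls in week 1.

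**3. How often the month alone excludes week 1**

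Assumptions, none of them given in the documents: vaccinations spread evenly over the 56 planned inclusion days (21 October to 15 December 2020), onset between D0 and D28, and day missing with month known. For each vaccination date v and onset day d, the event is provably late if (first day of the onset month − v) > 7. With uniform onset there are 56 × 29 = 1624 date pairs, and 387 are provably late: 387 / 1624 = 23.8%. The other two rows weight day d by 0.5^(d/7) or 0.5^(d/3).

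| Assumed onset pattern | True onset D8 to D28 | Provably after D7 from the month |
|---|---|---|
| Uniform | 72% (21/29) | 24% |
| Decay, 7-day half-life | 42% | 10% |
| Decay, 3-day half-life | 16% | 2% |

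These are shares of AEs with a missing day, not of all AEs.

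**4. The 28-day window**

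The V02 window runs to D35, so the same issue can arise at D28. For vaccination on 1 or 2 November, a December start is at least 30 or 29 days later. For 1, 2 or 3 December, a January start is at least 31, 30 or 29 days later. On these 5 of the 56 dates, a next-month start proves onset after D28. The current rule would keep such an event in the 28-day tables, although SAP 5.4.2.2 excludes a fully dated non-serious AE with onset after D28.

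**The case against.** The strongest reply is that the misplacement is not written into the SAP. The placement sentences belong to text on the 28-day and whole-study tables and refer to those tables. Nothing extends them to the 7-day summaries, and a programmer could equally leave undated events out. This stands: a reader might infer that the SAP instructs late events to be counted in week 1, and the documents do not support that. What remains is that the 7-day tables either inherit the only placement rule available, with the result shown above, or have no rule at all. Either way the SAP needs a definition.

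Two larger figures are also tempting.

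- A next-month start proves onset after D7 on 42 of the 56 planned vaccination dates (4 in October, 23 in November, 15 in December), or 75%. A reader might infer that three-quarters of undated events would be wrongly placed. The count is one of calendar dates, conditional on the partial date already naming the following month; it is not a share of events.
- With uniform onset, t = 8/29 of events fall in week 1. If a fraction p of all AEs is undated, the week-1 count rises by p(1 − t)/t: 2.6%, 5.2% or 13% for p = 1%, 2% or 5%. A reader might take this as the size of the error. It counts every undated late event, not only those provably late, and no p is given in the documents.

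Partial dates may well be few. Diaries are kept prospectively and reviewed at V02, gaps are clarified with the subject (Protocol 13.2), and SAEs are entered within 24 hours (Protocol 10.1). For non-serious AEs, the onset display already shows early clustering and a separate row for missing onset. SAP 5.4.2.3 gives SAEs no such display. Missing stop dates need no recording failure: an AE still ongoing at V02 has none.

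**Conclusion.** The point holds as a gap in the data-handling rules plus a contradiction between two SAP sections. The 7-day window is undefined for unsolicited AEs, SAEs and AESIs. The only rule that gives undated events a time would, if carried over, put some provably later events in week 1. SAP 5.4.4.1 and 5.4.2.2 disagree on whether a missing stop date makes onset missing, which could extend the problem to fully dated ongoing AEs.

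The number of events affected cannot be derived from the documents. The 2% to 24% range rests on assumed onset patterns and on partial dates that retain their month. The effect is probably small and is limited to descriptive safety tables with no testing. The rules are the same in both groups, no between-group bias is shown, and the primary immunogenicity analysis is untouched. It is worth correcting, but it is minor.

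**What to change.** Four changes to the SAP:

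1. In 5.4.2.2 and 5.4.2.3, define the 7-day period for unsolicited AEs and SAEs (and so AESIs, which are captured as SAEs) as a time of onset of 0 to 7 days. Refer to this definition in 4.7.2 and in the Table 6 footnote.
2. In 5.4.4.1, make onset depend on the start date and vaccination date only, as in 5.4.2.2. A missing stop date should affect duration alone.
3. Where month and year are known, exclude an event from a window when its earliest possible onset lies after that window. Apply this to the 7-day window and likewise to the 28-day window. Leave the whole-study rule as it is.
4. Show events whose onset cannot be determined on a separate line for unknown onset under the 7-day summary.

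The cost is a few sentences and minor programming. The small downside is that the 7-day count is no longer the most conservative possible, but a reader can add the separate line back to recover that figure.

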An unsolicited AE is an observed AE that does not fulfill the conditions prelisted in the CRB in terms of diagnosis and/or onset window post-vaccination. For example, if headache between D0 and D7 is a solicited reaction (i.e., prelisted in the protocol and CRB), then a headache starting on D7 is a solicited reaction, whereas headache starting on D8 post-vaccination is an unsolicited AE. Unsolicited AEs includes both serious (SAEs) and non-serious unsolicited AEs.

Injection Site Reaction:

An injection site reaction is an AR at and around the injection site. Injection site reactions are commonly inflammatory reactions. They are considered to be related to the product administered.

Systemic AE:

Systemic AEs are all AEs that are not injection or administration site reactions. They therefore include systemic manifestations such as headache, fever, as well as localized or topical manifestations that are not associated with the vaccination or administration site (e.g., erythema that is localized but that is not occurring at the injection site).

Adverse Event of Special Interest (AESI):

An AESI is one of scientific and medical concern specific to the Sponsor's product or program, for which ongoing monitoring and rapid communication by the investigator to the sponsor can be appropriate. Such an event might warrant further investigation in order to characterize and understand it. Depending on the nature of the event, rapid communication by the Sponsor to other parties (e.g., regulators) might also be warranted.

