9.2.2.2 Safety Endpoints

The secondary endpoint(s) for the evaluation of safety are:

- Occurrence, nature (Medical Dictionary for Regulatory Activities [MedDRA] preferred term [PT]), duration, intensity, and relationship to vaccination of any unsolicited systemic AEs reported in the 30 minutes after vaccination.
- Occurrence, time to onset, number of days of occurrence, maximum intensity, action taken, and whether the reaction led to early termination from the study, of solicited (prelisted in the subject's diary card and CRB) injection site reactions and systemic reactions occurring up to 7 days after vaccination.
- Occurrence, nature (MedDRA PT), time to onset, duration, intensity, relationship to vaccination (for systemic AEs only), and whether the event led to early termination from the study, of unsolicited AEs up to 28 days after vaccination.
- Occurrence, nature (MedDRA PT), time to onset, seriousness criteria, relationship to vaccination, outcome, and whether the event led to early termination from the study, of SAEs throughout the study.
- Occurrence, nature (MedDRA PT), and relationship to vaccination of AESIs throughout the study.

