9.2.2.3.3 Unsolicited Adverse Events

In addition to recording solicited reactions, subjects will be instructed to record any other medical events that may occur during the 28-day period after vaccination. Space will be provided in the diary card for this purpose. Information on SAEs will be collected and assessed throughout the study, from inclusion until 28 days (+ 7 days) after vaccination. Any SAE occurring at any time during the study will be reported by the Investigator in the CRB according to the completion instructions provided by the Sponsor; this includes checking the “Serious” box on the AE CRF and completing the appropriate Safety Complementary Information CRFs. All information concerning the SAE is to be reported either as part of the initial reporting or during follow-up reporting if relevant information became available later (e.g., outcome, medical history, results of investigations, copy of hospitalization reports). See [Section 10](#) for further details on SAE reporting.

For each unsolicited AE (whether serious or non-serious), the following information is to be recorded:

- Start and stop dates¹¹
- Intensity of the event:

For measurable unsolicited AEs that are part of the list of solicited reactions, the size of the AE as well as the temperature for fever will be collected and analyzed based on the corresponding scale used for solicited reactions (see [Table 1](#) and [Table 2](#)).

All other unsolicited AEs will be classified according to the following intensity scale:

- Grade 1: A type of AE that is usually transient and may require only minimal treatment or therapeutic intervention. The event does not generally interfere with usual activities of daily living.
- Grade 2: A type of AE that is usually alleviated with additional therapeutic intervention. The event interferes with usual activities of daily living, causing

¹¹ The stop date of all related AEs will be actively solicited. For other events, the investigator will provide the stop date when it becomes available. AEs for which no stop date was obtained during the course of the study will be considered as ongoing at the end of the study.

discomfort but poses no significant or permanent risk of harm to the research participant.

- Grade 3: A type of AE that interrupts usual activities of daily living, or significantly affects clinical status, or may require intensive therapeutic intervention.
- Whether the AE was related to the IP (for unsolicited systemic AEs)

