#### **5.4.2.2 Unsolicited Non-serious AEs**

Unsolicited AEs include non-serious unsolicited AEs and SAEs. This subsection only covers the endpoints for unsolicited non-serious AEs.

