##### ***Intensity***

The intensity for SAE will be computed using the same methodology than for unsolicited non-serious AEs described in [Section 5.4.2.2](#).

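### SAP 4.7.2 describes intensity, onset categories and duration only for non-serious unsolicited AEs, although the protocol endpoint includes serious ones; outside the immediate row, no Grade 3 count includes SAEs

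*SAP*

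**What the plan says.** **Definition.** Protocol 9.2.2.1 states: "Unsolicited AEs includes both serious (SAEs) and non-serious unsolicited AEs". SAP 5.4.2.2 agrees: "Unsolicited AEs include non-serious unsolicited AEs and SAEs".

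**Endpoint and planned analysis.** For unsolicited AEs up to 28 days, the secondary safety endpoint in Protocol 9.2.2.2 begins "Occurrence, nature (MedDRA PT), time to onset, duration, intensity, relationship to vaccination (for systemic AEs only". The matching analysis in Protocol 12.1.2.2 reads "Unsolicited AEs occurring within 28 days after the day of injection by system organ class (SOC) and PT, time to onset, duration, maximum intensity", with intensity graded 1 to 3. Neither text is limited to non-serious events.

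**Data.** Protocol 9.2.2.3.3 says "For each unsolicited AE (whether serious or non-serious), the following information is to be recorded". The list that follows includes start and stop dates and intensity.

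**SAP tables.** SAP 4.7.2 (Unsolicited AEs) plans: "The unsolicited non-serious AEs and ARs within 28 days after vaccine injection will also be summarized by maximum intensity, time of onset, and duration". In its row list, the any-and-Grade-3 split is attached to the immediate row and to three non-serious rows, the first of which begins "Unsolicited non-serious AE and AR (any and Grade 3". The row for all unsolicited AEs and ARs and the SAE row carry no grade. SAEs are summarised by SOC and PT, seriousness criterion and outcome. The footnote to SAP Table 6 adds counts within 7 days, within 28 days and during the study.

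**SAP derivations.** SAP 5.4.2.3 derives onset, duration and intensity for SAEs. On intensity it says: "The intensity for SAE will be computed using the same methodology than for unsolicited non-serious AEs".

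**Declared changes.** The SAP version history reports no major changes to the statistical analysis features, and SAP 5.2 lists none.

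**The concern.** The protocol asks how severe unsolicited AEs were, when they began and how long they lasted, and it counts serious events among them. The SAP answers those questions for non-serious events only. A reader who wants the number of subjects per vaccine with any Grade 3 unsolicited AE will not find it, except for the first 30 minutes. The derived SAE intensity and duration appear as a distribution in no listed table. At stake is a secondary descriptive endpoint that would be reported more narrowly than the protocol defines it, with no statement that it had been narrowed.

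**Working it through.** No figure in the plan is in dispute, so the check is a comparison of texts. I read the SAP's 28-day summary as using the same rows as its 7-day summary, because no separate row list is given.

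| Item | Protocol 12.1.2.2, unsolicited AEs | SAP, non-serious events | SAP, serious events |
|---|---|---|---|
| SOC and PT | Planned | Table 6 | Table 6, in the all-unsolicited and SAE tables |
| Maximum intensity | Planned, Grades 1 to 3 | Summarised | No distribution |
| Grade 3 count | Follows from maximum intensity | Three non-serious rows, plus the immediate row | Immediate row only |
| Time to onset | Planned (also in the SAE bullet) | D0-D3, D4-D7, D8-D14, ≥D15 | Cumulative counts: 7 days, 28 days, whole study |
| Duration | Planned | 1-3, 4-7, 8-14, ≥15 days | None |

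**Step 1: is the immediate row an exception?** Yes. Its label has no non-serious limit. SAP 5.4.4.1 rules out as immediate only those SAEs with missing or partially missing elapsed time, which implies that other SAEs can be immediate.

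**Step 2: can the missing Grade 3 total be rebuilt from the planned rows?** For one group and one period, let N be the subjects with a non-serious Grade 3 AE, S those with a serious Grade 3 AE, and B those with both. The count wanted is

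T = N + S − B.

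The SAP reports N and the number A of subjects with any SAE. It reports neither S nor B. Since S ≤ A, the rows give only N ≤ T ≤ N + A. Adding the SAE row to the non-serious Grade 3 row gives the upper bound: it includes SAEs below Grade 3 and counts twice any subject who has both kinds of event. Protocol 9.2.2.1 itself says that serious and severe are not synonymous, so A cannot stand in for S.

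**Step 3: how large could the difference be?** The documents give no Grade 3 or SAE rate. Purely as an illustration, take the planned 1050 per group (Protocol 5.1.1) and assume N = 5. The planned row shows 5/1050 = 0.48% (Clopper-Pearson 95% CI 0.15 to 1.11). Let k be the assumed number of subjects whose only Grade 3 event is serious. Then T = 5 + k, and the share absent from the non-serious row is k/(5 + k):

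| k | T/1050 | 95% CI | Share absent |
|---|---|---|---|
| 1 | 0.57% | 0.21 to 1.24 | 1/6 = 17% |
| 3 | 0.76% | 0.33 to 1.50 | 3/8 = 38% |
| 5 | 0.95% | 0.46 to 1.74 | 5/10 = 50% |
| 10 | 1.43% | 0.80 to 2.35 | 10/15 = 67% |

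The spread comes entirely from the assumed values of N and k. It shows only that a few events can move a small count, and it is not an estimate for this trial.

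**The case against.** The strongest defence is that the protocol has two tracks. Protocol 9.2.2.2 and 12.1.2.2 give SAEs their own bullet, which lists time to onset, seriousness criteria, relationship, outcome and early termination, but neither intensity nor duration. The SAP can be read as following that layout: grade and duration for non-serious events, seriousness and outcome for serious ones. Its rows are labelled as non-serious, the SAE row stands in the same table, and for a serious event the seriousness criterion and outcome carry much of what a grade would add. Safety is descriptive, with no hypotheses.

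Much of this stands. The gap for intensity and duration rests on the unsolicited-AE bullet read with the definition in Protocol 9.2.2.1, not on the SAE bullet. That reading is nevertheless the documents' own: both place SAEs among unsolicited AEs, and the unsolicited-AE bullet has no non-serious limit. For onset the defence is weaker, because the SAE bullet itself lists it.

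A reader might infer more than the documents support:

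- *Serious Grade 3 events vanish from the safety results.* They do not. They remain in the all-unsolicited-AE and SAE tables by SOC and PT, the seriousness and outcome summaries and the safety overview.
- *Every Grade 3 row excludes serious events.* The immediate row does not.
- *SAE onset and intensity reach no table.* Onset appears as cumulative counts. Intensity acts as a filter in the discontinuation tables, where SAP 5.4.2.4 requires at least Grade 1.
- *The Grade 3 rate is understated by a known share.* No event rate is given, and a labelled subset is not presented as a total.

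**Conclusion.** The point holds as an undeclared narrowing of a secondary safety endpoint. Followed as written, the SAP gives no count of subjects with any Grade 3 unsolicited AE that includes serious events, outside the 30-minute row. It gives no intensity or duration distribution for SAEs, and reports SAE onset only cumulatively. The size cannot be estimated from the documents.

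The conclusion rests on three things: that the shared definition brings SAEs into the unsolicited-AE endpoint, that the 28-day summary repeats the 7-day rows, and that the listed tables are the planned ones. The primary immunogenicity conclusion is untouched, and no decision rule depends on these tables. The change is still worth making, because a protocol-defined endpoint would otherwise be reported only in part.

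**What to change.** In SAP 4.7.2:

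1. Attach the any-and-Grade-3 split to the row for all unsolicited AEs and ARs, in both the 7-day and the 28-day summary.
2. Run the maximum-intensity, time-of-onset and duration summary on all unsolicited AEs and ARs, serious and non-serious, and keep the non-serious tables as a breakdown.
3. Add categorised time of onset to the SAE summary, for example with the categories already set in SAP 5.4.2.2.

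If the sponsor prefers to keep the restriction, SAP 5.2 should declare it as a change from the protocol-planned analysis, with the reason. That would make the departure visible but would not supply the missing counts.

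The cost is SAP wording and a few extra tables. Intensity and dates are already collected for serious and non-serious events, and SAP 5.4.2.3 already contains the SAE derivations.
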